**DATE: - 04/07/2022**

## **Introduction and Background**

Frozen shoulder is characterized by painful limitation of active and passive range of motion (ROM) of the shoulder. People describe pain, which can be severe, an inability to sleep on the affected side, loss of shoulder function in activities of daily living and limited movements that can lead to chronic stiffness.

Physiotherapy is one of the main treatments which aims to reduce pain, and regain mobility, muscle strength and optimal daily function. There is global loss of both passive and active ROM of the glenohumeral joint, with external rotation usually being the most restricted physiologic movement. Although frozen shoulder is frequently described as a self-limiting condition with gradual spontaneous recovery, the condition typically has mean duration of 30 months.

Individuals with primary frozen shoulder are commonly between 40 and 65 years old, and the incidence appears 4 times higher in females than males. The condition generally presents unilaterally with the non-dominant shoulder more commonly affected.

Frozen shoulder is “a condition difficult to define, difficult to treat, and difficult to explain from the point of view of pathology(Codman 1935) . The term adhesive capsulitis was introduced by Nevaiser to describe the inflamed and fibrotic condition of the capsule sticking to the humerus. But this term does not appear to appropriately describe the condition and arguably term should be abandoned as explained by Lundberg (1979).

The etiological explanation of frozen shoulder was directed toward two theories, contraction of the capsule and adhesions of the capsule which were running parallel. Some histological findings show that there is contraction of the capsule. In 1969, Lundberg came with the term frozen shoulder syndrome. In 2014, Jeremy Lewis came out with the term frozen shoulder contraction syndrome. It is likely that limitations in range of motion and the pain associated with frozen shoulder are not only related to capsular and ligamentous tightness, but also fascial restrictions, muscular tightness, and trigger points within the muscles. Physical therapists can address impairments and limitations associated each of these contributors to the pathology of frozen shoulder with a variety of treatment methods.

A meta-analysis suggested that glucocorticoid injections combined with exercise and manual therapy may provide improvement in range of motion .

Intensive mobilization may be more effective than other methods but mostly for late stages of the disease. Rehabilitation programs consisting of exercise, and modalities have been shown to improve shoulder ROM in all planes except external and internal rotation .

One study also showed that supervised neglect physical therapy worked better than intensive physical therapy .

A 2013 RCT showed short term improvement in function and range of motion in the painful phase using intra-articular corticosteroid . A 2016 study showed adding mobilisation to stretching patients had a long-term improvement in function and passive range of motion at one year follow up .

In a review of 31 studies in 2012, Maund et al concluded that there is limited clinical evidence on the effectiveness of treatments for primary frozen shoulder .

The UK FROST trial compared early structured physiotherapy, manipulation under anesthesia and arthroscopic capsular release. All three treatment options led to substantial improvements in pain and function and none of the treatments were superior to each other in the long term follow up

A recent study by Hollmann et al (2018) has demonstrated that muscle guarding may be a significant contributing factor to shoulder movement deficits in some patients suffering from frozen shoulder. In a sample of five patients with an indication for capsulotomy, they found that under general anesthesia, the movement of the affected shoulder was less restricted. All patients showed a significant increase in their passive range of motion (ROM), especially in abduction while under general anesthesia conditions, compared to their ROM while awake.

This finding supports the hypotheses that the fear of pain or the fact that little used tissue can be more easily damaged can produce a fear-based brain reaction and generate a muscle defense response that could lead to Frozen Shoulder. So, this may be the major contributing factor to movement restriction in some of these patients although more research is needed to determine the number of patients suffering from this type of Frozen shoulder.

One study by Donatelli et al shows promising results with low load prolonged stretch in frozen shoulder but there is no evidence for high load training.

An RCT by Annales et al showed that adding heavy load eccentric training resulted in a higher gain of isometric strength at 90 degrees of scapular abduction in subacromial impingement. Another study shows that a 12-week-isolated eccentric training program of the rotator cuff is beneficial for shoulder function and pain after 26 weeks in patients with rotator cuff tendinopathy. A systemic literature review shows that eccentric exercise may provide a small but likely not clinically important reduction in pain compared with other types of exercise in patients with subacromial impingement syndrome. But the load used on these studies were low. A systemic review by Kieren O sullivan shows eccentric training can improve strength and reduce the risk of injury in lower limb and facilitate increased muscle flexibility via sarcomerogenesis.

The forces applied during inferior glenohumeral mobilizations may vary between 3 to 14 kg (Witt 2016). A Japanese researcher Eiji Itoi (1993) found that 683 kg/cm^2 of force is required to stretch the posterior glenohumeral joint capsule. The heaviest dead lift is 472 kg (2018 world record) is still not enough to stretch the capsule. Most of the frozen shoulder contraction syndrome may be due to muscle inhibition, as the capsule cannot be stretched. So, exercise, stretching, mobilization procedures are suggested to decrease the muscle guarding.

This study focuses on the hypothesis that a heavy slow resistance exercises may have a role on muscle guarding in these cases. As there is evidence that frozen shoulder could be further complicated with muscle guarding which could further complicate the capsular adhesion, and hence a heavy slow resistance exercise is an effective therapeutic intervention which could control the muscle guarding status around the shoulder.

## **Objective**

The objective of this study is to compare the effect of heavy slow resistance exercises with conventional physical therapy alone for the management of frozen shoulder using double-blind randomized controlled trial design.

## **Methods**

The study will employ a double-blind randomized controlled study design. Ethical approval has been obtained from Kuwait Ministry of Health, Ethics committee. Written informed consent will be completed. Seventy patients both Kuwaitis and non-Kuwaitis with frozen shoulder attending the outpatient department of the Al Farwaniya hospital and PM& R hospital will be randomly assigned to the heavy slow resistance exercises group and the control group.

## **Sample size**

Shoulder external rotation range of motion is considered as the primary outcome measure for the proposed study. A study by Celik (2010) [24] was used to inform the sample size calculation, where the shoulder external rotation was measured at baseline and at 12-week post intervention for the glenohumeral range of motion exercise group. Using the means and standard deviations of 22 (12.5) degrees and 33 (14.9) degrees for external rotation range of motion changes resulted in an effect size of -0.799. With a two tailed hypothesis, the minimum required sample size is 30 patients per group at ( $\alpha$ ) 0.05 and a power (1-  $\beta$ ) of 85%. 35 participants per group will be recruited to account for attrition.

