## **Intervention**

Both groups will receive conventional therapy sessions which include active ROM exercise, strengthening and stretching exercises, end-range mobilization and hot packs (if indicated). Exercises will be given within the pain threshold limit twice a week for 12 weeks. In addition, the experimental group will receive heavy slow resistance exercise program using a theratube. The exact management approach will be standardized between the two groups in terms of intensity and frequency and the experimental group will only receive additional heavy slow resistance exercise.

Subjects will be assessed at baseline and at 3, 6, and 12 months. Shoulder external rotation and abduction ROM will be measured and compared within and between groups and will be analyzed using a One-way ANOVA.

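### The sample size uses a before-after gain in one exercise group as the difference between arms, so the stated 85% power is unsupported

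*Protocol*

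**What the plan says.** The Sample size section of the protocol sizes the trial on external rotation: "Shoulder external rotation range of motion is considered as the primary outcome measure for the proposed study". Its source is an earlier study "where the shoulder external rotation was measured at baseline and at 12-week post intervention for the glenohumeral range of motion exercise group". It continues: "Using the means and standard deviations of 22 (12.5) degrees and 33 (14.9) degrees for external rotation range of motion changes", reports an effect size of -0.799, and concludes that 30 patients per group give 85% power at two-sided alpha 0.05. It then adds: "35 participants per group will be recruited to account for attrition".

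The comparison of interest is between arms. The Objective is to "compare the effect of heavy slow resistance exercises with conventional physical therapy alone for the management of frozen shoulder". Under Intervention, "Both groups will receive conventional therapy sessions which include active ROM exercise, strengthening and stretching exercises", and "the experimental group will only receive additional heavy slow resistance exercise". The same section fixes the visits: "Subjects will be assessed at baseline and at 3, 6, and 12 months". No section gives an expected or target difference between the two arms.

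**The concern.** A two-group power calculation needs the difference expected between the groups at the time of analysis. As the protocol describes them, the two means are the start and end values of a single treated group. Their difference, 11 degrees, contains everything that happens to patients on an exercise programme over 12 weeks, including natural recovery. Most of that should also occur in this trial's control arm, which has active therapy of its own. What remains for the between-arm contrast is the added effect of heavy slow resistance exercise, and the cited figures carry no information on it.

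This calculation is the only justification given for 70 patients. If the added effect is well below 11 degrees, the trial has much less power than it claims. A non-significant result, read against a claimed 85%, could then be taken as evidence that the added exercise does nothing.

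**Working it through.** **Inputs from the Sample size section.** Means (SD) 22 (12.5) and 33 (14.9) degrees; two-sided alpha 0.05; power 85%; 30 per group, raised to 35 for attrition. No attrition rate is given; 5/35 implies about 14%.

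**1. Reproducing the protocol's figure.**
- Pooled SD = √[(12.5² + 14.9²)/2] = √[(156.25 + 222.01)/2] = 13.75.
- d = (22 − 33)/13.75 = −0.7999, which matches the stated −0.799.
- Two independent groups, two-sided 0.05, 85% power, noncentral t: n = 29.06, so 30 per group. Power is 84.9% at 29 and 86.1% at 30. The normal approximation gives 29.
- A paired before-after test would need 17 patients in total at an assumed baseline–follow-up correlation of 0.5 (31, 22 and 11 at correlations of 0, 0.3 and 0.7).

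So 30 per group comes from the two-independent-groups formula, with the baseline and 12-week values in place of the two arms.

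**2. What an 11-degree difference between arms would require.** If the control arm moved as the cited group did, from 22 to 33, the experimental arm would have to reach 33 + 11 = 44. That is a gain of 22 degrees, twice the cited gain.

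**3. The SD.** An unadjusted comparison of arms at 12 weeks depends on the spread at 12 weeks, 14.9. The pooled 13.75 mixes in the baseline SD.

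**4. Detectable difference at 85% power.** By noncentral t, the standardised difference detectable is 0.787 at 30 per group and 0.727 at 35. Multiplied by the SD:

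| SD | 30 per group | 35 per group |
|---|---|---|
| 14.9 | 11.7 degrees | 10.8 degrees |
| 13.75 | 10.8 degrees | 10.0 degrees |

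**5. Power at given between-arm differences.** The 8 and 5.5 degree values are assumptions for illustration; 5.5 is half of 11.

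| Difference | SD 14.9: power at 30 / 35 | n per group for 85% | SD 13.75: power at 30 / 35 | n per group for 85% |
|---|---|---|---|---|
| 11 | 80% / 86% | 34 | 86% / 91% | 30 |
| 8 | 53% / 60% | 64 | 60% / 67% | 55 |
| 5.5 | 29% / 33% | 133 | 33% / 38% | 114 |

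**6. Sensitivity to the analysis.**
- Adjusting for baseline gives SD = 14.9 × √(1 − r²). At 30 per group the detectable difference is then about 11.2, 10.2 and 8.4 degrees for assumed r of 0.3, 0.5 and 0.7.
- Analysing change scores gives SD = √(12.5² + 14.9² − 2r × 12.5 × 14.9), that is 16.3 to 10.8 for r of 0.3 to 0.7. Power at 5.5 degrees with 30 per group is then 25% to 49%.

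**The case against.** **The figures may be change scores.** The protocol attaches the word changes to the two means. If they were the changes in two different groups, the calculation would be a legitimate between-group one, and the source cannot be checked here. However, the preceding sentence names one group and two time points, and no second group appears. The conclusion is therefore about what the protocol says. If the sponsor meant something else, the comparison group still has to be named.

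**Within-group comparisons are also planned.** The Intervention section says range of motion will be compared both within and between groups, and a before-after effect is relevant to the former. That is true, but the objective is comparative and the size is stated per group from a two-group formula. The within-group aim does not rescue the between-arm power.

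**The exact percentages depend on the chosen SD.** This stands. With 13.75 instead of 14.9, power at 30 per group is 60% rather than 53% at 8 degrees, and 33% rather than 29% at 5.5. Even with 14.9, all 35 per group evaluable would give 86% at 11 degrees. The central criticism survives either SD.

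**Baseline adjustment could recover power.** It could, but the protocol specifies one-way ANOVA and mentions no adjustment.

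**The time point can be inferred.** Twelve weeks of treatment and a 12-week source point to the 3-month visit. This stands; naming the visit is a small clarification, not a separate defect.

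**No shortfall is proven.** Also correct. The claim is shown to be unsupported; the trial is not shown to be underpowered.

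**Conclusion.** The concern holds. As the protocol describes it, the effect size of -0.799 is a within-group change over time, used as though it were a difference between two randomised arms that both receive active therapy. The stated 85% applies only if the added exercise yields roughly 11 degrees more external rotation than conventional therapy, and nothing in the protocol supports a difference of that size. Taking the 12-week SD of 14.9, 70 patients suit only large differences: 11.7 degrees at 30 evaluable per group, or 10.8 at 35.

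True power cannot be computed from the document. The powers at 8 and 5.5 degrees, and the correlations used in the sensitivity checks, are assumptions. The 22-degree figure assumes that this control arm would repeat the cited group's gain, although its programme is not necessarily the same. Because this is the sole basis for the trial's size, the paragraph needs correcting.

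**What to change.** Remove the statement that the before-after effect size gives 85% power for the group comparison. Keep 70 patients and say what that number can detect, for example:

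> With 30 evaluable patients per group, an SD of 14.9 degrees and two-sided alpha 0.05, the trial has 85% power for a between-group difference of about 11.7 degrees in external rotation at 3 months, or about 10.8 degrees if all 35 per group are evaluable. With 30 per group, power is about 80% at 11 degrees, 53% at 8 and 29% at 5.5.

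Beside this, state the between-arm difference the sponsor wants to detect and why, or say that no estimate of the added effect was available. If a baseline-adjusted analysis is adopted, give the adjusted detectable difference with its assumed correlation instead (about 10.2 degrees at 30 per group for r = 0.5). It would also help to say that a non-significant result will not be read as showing no effect.

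The cost is one reworded paragraph, with no extra patients or visits and no change of design. The stated power becomes less favourable, and readers will see that the trial covers only large differences. Rewording does not remove any underpowering; it makes it visible.

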**Data analysis**

SPSS will be used for statistical analysis. All outcome measures will be analyzed using one-way ANOVA.

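### The one-way ANOVA fixed for every outcome cannot use earlier visits, so selective loss after 3 months could bias the 6- and 12-month arm comparisons

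*Protocol*

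**What the plan says.** Protocol, Sample size, plans on external rotation: "Shoulder external rotation range of motion is considered as the primary outcome measure for the proposed study". The calculation ends with "With a two tailed hypothesis, the minimum required sample size is 30 patients per group", and then "35 participants per group will be recruited to account for attrition". Attrition appears nowhere else, and no rate, timing or reason for loss is given.

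Protocol, Intervention, sets the schedule: "Subjects will be assessed at baseline and at 3, 6, and 12 months". Treatment lasts 12 weeks, so the 6- and 12-month visits fall well after it ends. The same section names one-way ANOVA for range of motion. Protocol, Data analysis, extends it to everything: "All outcome measures will be analyzed using one-way ANOVA".

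The protocol does not say that only completers are analysed, and it does not say how absent values are treated.

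**The concern.** Recruiting more patients replaces lost precision. It does not make those who stay representative of those randomised.

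A one-way ANOVA has a single factor and no patient term. With arm as the factor, it compares the arms at one visit (or on one change score) at a time. What is known at 3 months about someone who later stops attending cannot enter the 12-month comparison. Pooling all visits in one such ANOVA would not help, because repeated values from one patient would then be treated as independent.

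The protocol's introduction notes that the condition is often described as self-limiting. Whether a patient returns at 6 or 12 months may plausibly depend on how the shoulder was at 3 months. If that dependence differs between arms, the comparison of attenders is distorted, even though the trial holds data that could correct it. A missing-data section may be left to the SAP. The named method is different: the protocol fixes it, and an SAP that adopted a longitudinal model would contradict the protocol.

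**Working it through.** **1. The plan's own figure.** Inputs from Protocol, Sample size: "Using the means and standard deviations of 22 (12.5) degrees and 33 (14.9) degrees", two-sided alpha 0.05, power 85%.

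- Pooled SD = √((12.5² + 14.9²)/2) = √189.13 = 13.75 degrees.
- Effect size = (33 − 22)/13.75 = 0.80 in absolute value; the protocol gives 0.799.
- Exact t-test power at 0.799 is 84.8% with 29 per arm and 86.1% with 30, so 30 per arm reproduces.
- Allowed loss = 1 − 30/35 = 14.3%.

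The sample size is not in error on this point.

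**2. Bias when only attenders are compared.** Let z be the standardised 3-month value, ρ its correlation with the 12-month value, and log-odds of loss after 3 months = a + bz, with a set to give the chosen loss rate. Let m be the mean of z among those who stay. Then

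bias in the 12-month arm difference = ρ × SD × (m in experimental − m in control).

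None of the following is in the protocol, so all are assumptions: SD 14 (the planning SD of 13.75, rounded); ρ = 0.5 to 0.7; b = 0.5 (weak) or 1.5 (strong) per SD. At 14.3% loss, strong selection means that a patient 1 SD towards the side that tends to leave is lost with probability 28%, against 2% for one 1 SD the other way. Under weak selection these are 20% and about 8.5%.

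Numerical integration gives the size of m as 0.069 (b = 0.5, 14.3% loss), 0.168 (b = 1.5, 14.3%), 0.065 (b = 1.5, 5%) and 0.277 (b = 1.5, 25%).

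| Loss pattern | ρ = 0.5 | ρ = 0.7 | Share of 11 degrees |
|---|---|---|---|
| Opposite kinds, 14.3% per arm, weak | 2 × 0.069 × 7 = 1.0 | 2 × 0.069 × 9.8 = 1.4 | 9–12% |
| Opposite kinds, 14.3% per arm, strong | 2 × 0.168 × 7 = 2.3 | 2 × 0.168 × 9.8 = 3.3 | 21–30% |
| Same kind, 5% vs 25%, strong | (0.277 − 0.065) × 7 = 1.5 | (0.277 − 0.065) × 9.8 = 2.1 | 13–19% |
| Same kind, same rate | 0 | 0 | 0 |

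(7 = 0.5 × 14 and 9.8 = 0.7 × 14.) Simulated trials with 35 per arm agree: 1.0 to 1.4, 2.3 to 3.3 and 1.6 to 2.0 degrees for the first three rows.

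**3. Direction and error rate.** In the opposite-kinds scenario simulated, poor results leave control and good results leave the experimental arm, so the bias runs against the experimental treatment. The mirror pattern would favour it. With no true effect, the attender-only test rejects in about 10% to 16% of trials under strong selection and about 6% under weak selection, instead of 5%. In the simulated direction the excess is false evidence for control.

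**4. What the earlier visit recovers.** Predicting the 12-month value from the 3-month value within each arm, and averaging over all randomised patients, leaves about 0.1 degree or less in every scenario above. If loss depends instead on the unseen 12-month value (opposite kinds, 14.3%, SD 13.75, log-odds 1 to 2 per SD), the bias is 3.5 to 5.5 degrees without the 3-month data and 1.9 to 4.3 degrees with it.

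**The case against.** The strongest reply is that the protocol never commits to a completers-only analysis. Imputation before the ANOVA is compatible with its text, and missing-data rules commonly sit in an SAP, which is not shown here. This stands. A reader might infer that the plan fixes an attenders-only analysis, or that a missing-data rule has been wrongly omitted. The documents support neither. What remains is that the named ANOVA itself makes no use of earlier visits.

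A reader might also infer that the later comparisons will be biased. That does not follow. Bias needs loss that differs between arms in amount or kind. A self-limiting condition and the end of treatment would tend to remove the same kind of patient from both arms. Protocol, Randomization/Blinding, says patients are blinded, which, if achieved, makes opposite-kinds loss less likely. Opposite kinds are not essential, however: unequal rates of the same kind are enough.

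The figures depend on assumed selection, and the strong case is the unfavourable end of the selection strengths in the table. Enlarging the sample for attrition is ordinary practice, and the protocol does not claim that it deals with bias. Finally, the trial is sized on 12-week data and no section makes 6 or 12 months primary. Loss after 3 months leaves the 3-month comparison untouched.

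**Conclusion.** The point holds in conditional form. The protocol fixes a between-arm method that cannot use earlier visits in a four-visit trial that expects attrition. Without prior imputation, the 6- and 12-month comparisons are therefore open to bias from selective loss. Under the stated assumptions, the size at 12 months runs from about zero (loss alike in both arms) to about 3.3 degrees, or 30% of the planning difference (strong, opposite-kinds selection at the 14.3% the plan allows for).

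The dropout pattern, selection strength and correlation are all assumed, so these figures show what could happen and do not predict it. The change is worth making because the better method costs little, not because bias has been shown.

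**What to change.** In Protocol, Intervention and Data analysis, replace one-way ANOVA for between-arm comparisons with one likelihood-based repeated-measures mixed model per outcome. Its terms are arm, visit, arm-by-visit and the baseline value, with an unstructured covariance across visits. Include every randomised patient in the assigned arm with whatever visits are available. Report the arm contrast at each visit, and attendance by arm and visit.

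The cost is a change of wording and slightly more analysis work. SPSS, already named, fits the model, and no new data or patients are needed. The limits should be stated: the model removes the bias only if loss depends on observed values, reduces it in part otherwise, and has no 3-month information for patients lost before that visit.
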